Design: To address the impact of a popular, over-the-counter gel lubricant use in MSM on PrEP, investigators at Emory University will collaborate with the Centers for Disease Control and Prevention (CDC) to conduct a randomized clinical trial of 90 MSM. Men will be randomized into a 3-arm study as follows: (1) daily oral Truvada® only, (2) daily gel lubricant applied rectally only or (3) oral Truvada® plus rectal gel lubricant application daily. This study will entail 4 study visits at the Emory University Hope Clinic. During the first visit (time 0), all men will be screened for eligibility and undergo written informed consent, physical examination, rapid HIV testing, phlebotomy for screening laboratories, and randomization. During study visit 2 prior to the initiation of study product (time 1-6 weeks), participants will undergo phlebotomy, collection of rectal secretions, and rectal biopsy via rigid sigmoidoscopy for establishment of baseline values. During study visit 3 (time 4-16 weeks), men will be dispensed and instructed on the at-home application of rectal lubricant and/or oral Truvada. During study visit 4 (time 5-26 weeks), men will return after 7 consecutive days of study product use for repeat phlebotomy, collection of rectal secretions, and rectal biopsy via rigid sigmoidoscopy. After collection, biologic specimens will be immediately transported by courier to CDC (laboratory of [name]) for processing. Specimens will be processed immediately for *ex vivo* laboratory assays that will include PrEP drug concentrations, inflammatory cytokine levels, HIV target cell measurement and characterization by flow cytometry, and *in vitro* HIV infection assays. Comparison of assay results among the 3 study arms should determine if rectal lubricant usage reduces PrEP drug concentrations, increases inflammation, or increases the proportion or susceptibility of HIV target cells in the rectal mucosa.

Duration: The duration of this study is 2 years. Participants will be considered 'on-study' for no more than 26 weeks.

Sample size: For this protocol we will recruit 90 HIV-negative MSM who meet eligibility criteria outlined in the protocol.

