The efficacy reported in clinical studies of daily oral dosing of Truvada® or tenofovir to prevent HIV infection in MSM indicates the potential for PrEP to greatly reduce HIV infections within these high-risk populations. CDC recently released clinical practice guidelines recommending PrEP for MSM at risk of HIV infection.¹ However, the impact of rectal lubricant use on factors that could impact PrEP effectiveness in MSM is unclear. Recent studies suggest that lubricant application can increase epithelial damage and expression of inflammatory makers in human rectal tissue explants and epithelial cell cultures, and in macaque monkey rectal models without increasing their rates of HIV or SHIV infection, respectively.²⁻⁴ In contrast, consistent rectal lubricant use has been shown to increase acquisition of non-HIV STDs in a cohort of MSM in the USA.⁵ Additionally, studies from the TDF2 Study have suggested that ratios of intracellular tenofovir to natural substrate are reduced in the presence of immune cell activation. Together, these studies raise the concern that while MSM taking oral PrEP may be protected from HIV acquisition, regular use of rectal lubricants may abrogate the protection provided by PrEP due to increased epithelial damage, inflammation and immune activation.

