To address the impact of a popular, over the counter, gel lubricant use in the rectum in MSM on PrEP, investigators at Emory University will collaborate with [name] at the CDC to recruit and randomize 90 MSM into a three-arm study of PrEP and lubricants: (1) daily oral Truvada® for 7 days, (2) daily gel lubricant applied rectally for 7 days or (3) oral Truvada® plus rectal gel lubricant application daily for 7 days. At CDC, *ex vivo* laboratory assays will be used to evaluate the impact of rectal lubricant use on oral PrEP's effectiveness. Blood, rectal secretions and rectal biopsies obtained by rigid sigmoidoscopy (at approximately 8 -10 cm from the anal verge) will be collected from men in all three study arms at least 21 days prior to initiation of treatment and immediately following 7 days of consecutive use of assigned product. Specimens will be processed immediately for *ex vivo* laboratory assays at CDC. Blood plasma and PBMCs will be used to measure extracellular and intracellular drug concentrations as well as intracellular concentrations of the natural dNTP substrates to assess adherence to oral Truvada® and to compare changes in the ratio of drug to natural substrate in peripheral blood. Rectal secretions from all participants will be analyzed to measure changes in soluble immunological cytokines in the presence of gel lubricant usage that may indicate associated increases in inflammation. Rectal lymphocytes will be isolated from the rectal biopsies collected from each man and analyzed for concentrations of intracellular tenofovir and emtricitabine as well as natural substrates, dATP and dCTP, to evaluate the potential for gel lubricant to alter the ratio of antiretroviral drug to natural substrate in the rectal mucosa. Additionally, rectal lymphocytes from 10 participants in each arm will be characterized using multicolor flow cytometry to observe potential changes in the proportion and activation state of HIV target cells within the rectal mucosa. Rectal lymphocytes from the remaining 10 participants in each arm will be subjected to *in vitro* infection with HIV to test for changes in the susceptibility to virus infection in the presence of gel lubricant usage.

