Study visit 4 will occur a minimum of 1 week after study visit 3 and a maximum of 26 weeks from the screening visit. As above, men will be provided an appointment for study visit 4 during study visit 3. They will be instructed to use study product based on arm assignment for 7 consecutive days prior to the study visit 4 appointment. During study visit 4, the participant will undergo a 60mL peripheral blood draw. A urine sample will be collected from participants randomized to an arm containing Truvada. This sample will be used to at CDC to develop an assay to detect Truvada in the urine. All specimens will be coded with a unique numeric identifier such that the CDC laboratories that receive the specimens will be unable to link them

back to the study participants. Finally, rigid sigmoidoscopy (described further below) will be performed and, rectal secretions will be collected with Dacron swabs, and 8-12 rectal biopsies will be collected. An additional swab will be collected for testing for gonorrhea, chlamydia, and HSV-2 DNA to be performed by CDC. If positive for gonorrhea or chlamydia, men will be referred for care at their private physician's office, the health department, or AID Atlanta for treatment. HSV-2 results will not be returned to participants given the unclear clinical utility of HSV-2 serology in the absence of active disease. All men will be instructed to place nothing in the rectum and to abstain from sex for 7 days after the procedure to allow the mucosa to heal.

Contingency visit:

Attempts to ensure adherence to the study visits will be made with telephone and/or email reminders to the participant. However, if screening laboratory results are lost or are inconclusive or if a participant has been unable to adhere to study protocol, he may be rescheduled for a future date where the above visit procedures will be performed. These additional visits will be scheduled within the above visit windows.

Phone calls/retention contacts:

[figure not shown]
While on study, periodic phone calls, texts, or email reminders will occur between study staff and participants to ensure proper retention and adherence to study protocol.

Rectal biopsy procedures

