TITLE OF PROJECT: PrEP, LUBE, AND THE RECTAL MUCOSA IN MSM AT RISK OF HIV

Emory IRB00077593

NCT02401230

PRINCIPAL INVESTIGATOR: [name], MPH

19Jan2018

STATISTICAL ANALYSIS PLAN

Drug and dNTP concentrations were normalized to fmol/million cells and fmol/mg rectal tissue in blood and tissue, respectively. Detectable drug and dNTP concentrations as well as immune cell proportions were compared between the Truvada, Rectal Gel Lubricant and Rectal Gel Lubricant + Truvada study arms using a Wilcoxon Rank Sum Test. Left censoring was observed for drug concentration measurements below the limit of detection.

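### The protocol plans plasma and PBMC drug levels partly to assess adherence, but the SAP gives blood only a per-cell unit and specifies no plasma or adherence analysis

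*SAP*

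**What the plan says.** Protocol, Project Description: "Blood plasma and PBMCs will be used to measure extracellular and intracellular drug concentrations as well as intracellular concentrations of the natural dNTP substrates". The same sentence gives the purpose: "to assess adherence to oral Truvada® and to compare changes in the ratio of drug to natural substrate in peripheral blood". Plasma and PBMCs are named jointly for both uses.

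SAP, Statistical Analysis Plan (a single paragraph): "Drug and dNTP concentrations were normalized to fmol/million cells and fmol/mg rectal tissue in blood and tissue, respectively". The comparison that follows is: "Detectable drug and dNTP concentrations as well as immune cell proportions were compared between the Truvada, Rectal Gel Lubricant and Rectal Gel Lubricant + Truvada". The method is a Wilcoxon rank sum test. The paragraph ends by noting left censoring of drug values below the limit of detection. Plasma, adherence and the drug-to-substrate ratio are not mentioned.

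On dosing, the protocol's Design paragraph says that at visit 3 "men will be dispensed and instructed on the at-home application of rectal lubricant and/or oral Truvada". Visit 1 states that the study is not blinded. The section on phone calls and retention contacts provides that "periodic phone calls, texts, or email reminders will occur between study staff and participants to ensure proper retention and adherence to study protocol". At visit 4, men in the Truvada arms also give urine: "This sample will be used to at CDC to develop an assay to detect Truvada in the urine".

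**The concern.** The contrast between Truvada alone and Truvada plus lubricant carries the pharmacological question. In that contrast a low drug value in blood cells has two possible readings. The men may have taken fewer pills, which says nothing about lubricant. Or they may have taken the pills and carried less drug in their cells, which would matter for the trial's question. One arm manages a daily rectal product as well as a daily tablet and everyone knows his assignment, so adherence could differ by arm. The documents give no figure for how likely that is.

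The protocol anticipates the problem by giving the blood measurements an adherence purpose. The SAP does not carry that purpose through. The same gap affects the tissue comparison, because missed pills would lower rectal drug levels too.

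**Working it through.** **1. What each document provides for blood.** There is no plan figure to reproduce, so the first step is to set the texts side by side.

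| Item | Protocol | SAP |
|---|---|---|
| Intracellular drug and dNTP (PBMC) | planned | fmol/million cells, rank sum test |
| Extracellular drug (plasma) | planned | no unit, no named analysis |
| Adherence to Truvada | stated purpose | not mentioned |
| Drug-to-substrate ratio in blood | stated purpose | not mentioned |

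Plasma has no cell denominator, so the SAP's blood unit cannot apply to it. The protocol has no statistics section that fills the gap.

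**2. Is adherence measured in some other way?** No pill count, diary or observed dosing is described. Reminders support adherence but do not measure it. Urine is collected for assay development and is not named as an adherence measure.

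**3. Can the per-cell value alone separate the two readings?** Take a simple model: level = f × Σ 0.5^(t/h), summed over the doses taken, where t is hours from dose to sampling, h the half-life and f the intracellular conversion factor. Assumptions: seven daily doses, sampling 24 h after the seventh (t = 24, 48, ..., 168 h), mono-exponential decay.

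Example with h = 72 h and f = 1:
- all doses: 0.794 + 0.630 + 0.500 + 0.397 + 0.315 + 0.250 + 0.198 = 3.084
- last dose missed: 3.084 − 0.794 = 2.290, and 2.290/3.084 = 0.743, a fall of 26%

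Full adherence with f = 0.743 gives exactly the same value. The equivalence holds for any half-life and any pattern of missed doses. Dividing by dNTP does not break it, because missed doses lower the numerator of the ratio as well.

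**4. What would plasma add?** The documents give no half-lives. I assume 10-17 h for plasma and 36-120 h inside cells. The percentage fall from full adherence at 24 h is Σ(missed terms)/Σ(all terms). For full adherence sampled 12 h later it is 1 − 0.5^(12/h).

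| Half-life | Last dose missed | Doses 1-2 missed | Doses 3-5 missed | All taken, sampled at 36 h |
|---|---|---|---|---|
| 10 h (plasma) | 81% | 0% | 4% | 56% |
| 17 h (plasma) | 62% | 1% | 13% | 39% |
| 36 h (cells) | 39% | 6% | 31% | 21% |
| 72 h (cells) | 26% | 15% | 39% | 11% |
| 120 h (cells) | 21% | 19% | 42% | 7% |

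Plasma responds strongly to a missed last dose, hardly at all to doses missed earlier, and strongly to the time since the last dose. The documents fix no interval from last dose to sampling.

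**5. Numbers available.** Study Population expects 60 completers, so 60/3 = 20 per arm. The Design paragraph's total of 90 gives 90/3 = 30 randomised per arm. Splitting either Truvada arm by plasma level leaves small groups.

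**The case against.** The strongest reply is that the SAP is silent on plasma and does not exclude it. Its first sentence is a normalisation rule; plasma is already expressed per volume and needs no cell normalisation. Its comparison sentence names no matrix. A reader might infer that plasma was never analysed or was discarded, and the documents do not show that. What they show is that no plasma unit, plasma analysis or adherence use is specified.

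A reader might also take plasma to be the protocol's designated adherence measure. It is not: plasma and PBMCs share that role, and an undetectable PBMC level would still reveal gross non-adherence. The ambiguity concerns partial adherence among men with detectable drug, and those are the values that the SAP says it compares.

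A third tempting step is to say that the protocol expects the mechanism to lower PBMC drug. The background reports only a suggestion that "ratios of intracellular tenofovir to natural substrate are reduced in the presence of immune cell activation". A ratio can fall because dNTP rises while drug per million cells is unchanged, and the main question concerns the rectum. Altered intracellular drug is thus a possible reading of a PBMC difference, not one that the documents establish.

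Finally, plasma is an imperfect check, as the table above shows. That stands, and it limits what the fix can claim. None of these points supplies the missing adherence analysis.

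**Conclusion.** The concern holds as a gap between the protocol's stated purpose for the blood measurements and the SAP's analysis. With home dosing, no blinding and no other adherence measure described, a lower PBMC drug value in the Truvada plus lubricant arm would not by itself support a lubricant effect. This limits interpretation of a main comparison; it does not invalidate the trial.

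The illustrative size is a 21-39% fall in the per-cell level from one missed final dose, against 62-81% in plasma. These figures rest on the assumed half-lives, 24 h sampling and mono-exponential decay. The argument that the per-cell value cannot separate the two readings does not depend on the half-lives chosen.

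A reader might infer that a PBMC difference which persists after stratifying by plasma can be credited to lubricant. It cannot. Men who missed doses 3-5 would have nearly normal plasma (4-13% lower) and clearly lower cell levels (31-42% lower). Full adherence with sampling 12 h later would lower plasma by 39-56%. The strata would also be defined after randomisation.

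**What to change.** In the SAP:

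- Report visit 4 plasma tenofovir and emtricitabine per mL, including values below the limit of detection, since those are the clearest sign of missed dosing.
- Compare them between the two Truvada arms with a rank test, as an adherence check presented beside the PBMC results.
- Keep PBMC drug and dNTP in fmol/million cells as the pharmacological outcome.
- Label any PBMC comparison restricted or stratified by plasma level as supportive only, and state that persistence after stratification does not by itself attribute a difference to lubricant.
- If the plasma measure was dropped, say so, and limit the blood conclusion to a difference in PBMC drug that may reflect adherence.

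The cost is SAP wording and one or two more reported comparisons. The protocol already plans the plasma assays, so no new samples are needed. The remaining limit is that plasma says little about doses missed earlier in the week.

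### The SAP plans no analysis of the drug-to-natural-substrate ratio, one of the protocol's stated pharmacological aims

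*SAP*

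**What the plan says.** **Protocol, Project Description.** The rationale cites a study suggesting that "ratios of intracellular tenofovir to natural substrate are reduced in the presence of immune cell activation". Blood plasma and PBMC assays serve to assess adherence and "to compare changes in the ratio of drug to natural substrate in peripheral blood". For the rectum, "Rectal lymphocytes will be isolated from the rectal biopsies collected from each man" and assayed for tenofovir, emtricitabine, dATP and dCTP, "to evaluate the potential for gel lubricant to alter the ratio of antiretroviral drug to natural substrate in the rectal mucosa". The same section says that the pharmacological analyses will show whether lubricant lowers this ratio in rectal HIV target cells, and links that to PrEP effectiveness.

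**Protocol, Design and Lay Summary.** Here the question is put more simply: does lubricant reduce PrEP drug concentrations or levels? No ratio is mentioned.

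**SAP.** This is one paragraph, in the past tense, dated 19Jan2018. Its three statements are:
- On units: "Drug and dNTP concentrations were normalized to fmol/million cells and fmol/mg rectal tissue in blood and tissue, respectively".
- On the variables compared and the method: "Detectable drug and dNTP concentrations as well as immune cell proportions were compared between the Truvada", lubricant-only and combined arms, with a Wilcoxon rank sum test.
- On values too low to measure: "Left censoring was observed for drug concentration measurements below the limit of detection".

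No ratio is derived or compared.

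**The concern.** A ratio can move when neither component moves much, and can stand still when both move. Separate comparisons of drug and of dNTP therefore do not settle whether the ratio changed, or by how much. If the SAP is the whole analysis, a question that the protocol ties to PrEP effectiveness has no planned answer, although both analytes were to be measured. A reader would have to infer the ratio from two comparisons, neither designed for it. A ratio added after the results are known, without a label and a stated rule for undetectable drug, would also be hard to interpret.

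**Working it through.** **1. Text against text.**

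| Question in the protocol | Where | Analysis in the SAP |
|---|---|---|
| Are drug concentrations lower with lubricant? | Design; Lay Summary | Yes, drug concentrations compared |
| Does the drug-to-substrate ratio change in blood? | Project Description | None |
| Does it change in rectal mucosa or target cells? | Project Description | None |

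The SAP's dNTP comparison can flag a change in the denominator, but does not estimate the ratio. The documents give no alpha, power, SD or effect size, so there is no planned figure to reproduce.

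**2. Why two tests do not replace one ratio.** Let D be drug and S be substrate, on the log scale. The arm difference in log ratio is Δ(D) − Δ(S). With a common log-SD σ and correlation ρ, the SD of the log ratio is σ√(2(1 − ρ)). For σ = 0.7 this is 0.99 at ρ = 0, 0.70 at ρ = 0.5 and 0.54 at ρ = 0.7.

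**3. Illustration.** Per-arm numbers come from the protocol: 10 men per arm for flow cytometry plus "Rectal lymphocytes from the remaining 10 participants in each arm" for infection assays gives 20, which matches 60 completers / 3. Assumed, because the documents give none: σ = 0.7, ρ from 0 to 0.7, two-sided 0.05, the shifts below, and all values detected. The figures are rejection rates of Wilcoxon rank sum tests, Truvada against Truvada + lubricant, by Monte Carlo with 10,000 replicates per setting.

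| Shift with lubricant | True ratio of ratios | Drug test | dNTP test | Ratio test |
|---|---|---|---|---|
| Drug ×0.64, dNTP ×0.64 | 1.00 | 48% | about 48% | 5% |
| dNTP ×1.78 only | 1/1.78 = 0.56 | 5% | 69–70% | 41–90% |
| Drug ×0.75, dNTP ×1.33 | 0.75/1.33 = 0.56 | about 23% | about 23% | 41–89% |
| Drug ×0.56 only | 0.56 | 69–70% | 5% | 41–88% |

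In row 1 the standardised drug shift is ln(0.64)/0.7 = −0.64, while the log-ratio shift is zero. In row 2 the dNTP shift is ln(1.78)/0.7 = 0.82 SD. The ratio shift is 0.577/0.99 = 0.58 SD at ρ = 0, 0.82 at ρ = 0.5 and 0.577/0.54 = 1.06 at ρ = 0.7. So the dNTP test has more power below ρ = 0.5, the two tie there, and the ratio test has more above it.

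The Design section gives 90 men. With 10–15% loss that is 90 × 0.85 / 3 = 25.5 to 90 × 0.90 / 3 = 27 per arm. The drug test in row 1 then rejects in 56–61%, and the ratio test stays at about 5%.

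**4. Undetectable drug.** The SAP reports values below the limit of detection (LOD), so a ratio needs a rule. Take row 1 (true ratio of ratios 1.00) with an assumed 15% or 30% undetectable in the Truvada arm, which implies about 35% or 55% in the combined arm.

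| Rule | False positives at 15% | At 30% |
|---|---|---|
| Rank undetectable samples lowest | 10–13% | 19–23% |
| Use detectable pairs only | 5–9% | 6–10% |
| Gehan's test, bound LOD/dNTP | 5–6% | 6–7% |
| Joint censored log-normal model | 5% | 5% |

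Lowest rank fails because an undetectable drug value over a small dNTP need not be a small ratio. Dropping samples also costs power: in row 4, detectable pairs give 13–62% (15% undetectable) against 45–88% for Gehan's test. A censored model fitted to the ratio alone is biased, because its bound contains the same dNTP: the median estimate is 0.92–0.96 at 15% and 0.86–0.94 at 30%. The joint model gives 0.99–1.00 and 1.00–1.01.

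**The case against.** **The ratio is not the only question.** A reader might infer that the SAP misses the protocol's pharmacological question altogether. The documents do not support that. The Design section and Lay Summary ask about drug concentrations or levels, and adherence is a further stated purpose of the blood assays. In row 1, a 48% rejection rate for drug is a correct answer to the concentration question. This stands, and limits the point to one aim among several.

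**Silence may be brevity.** The SAP also omits the cytokine and in vitro infection analyses that the protocol describes. One might infer that no ratio was ever analysed, or that only p-values were reported. Neither follows: the SAP names a test, does not describe the reporting, and says nothing about work outside it. The omission from the text is certain; what was done is unknown.

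**The numbers show no general loss of power.** This also stands. Every SD, correlation, shift and undetectable share is assumed, and below a correlation of about 0.5 a separate test can have more power than the ratio test. The illustration shows only that the separate tests answer a different question.

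**The rectal specimen is a separate matter.** In part. Expressing drug and dNTP per the same unit cancels in a within-sample ratio, so the unit alone does no harm. But the protocol describes isolated lymphocytes and the SAP describes amounts per mg of rectal tissue. If whole tissue was assayed, even a correct ratio only partly meets the aim concerning HIV target cells.

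**Conclusion.** The point holds as a gap between a stated aim and the planned analysis, and should be fixed. The Project Description makes the drug-to-substrate ratio an explicit aim in blood and rectum, and the SAP as written provides no test, estimate or interval for it. That rests on the text alone and is secure. The size of any consequence is not known: the contrast of 48% with 5% depends on an assumed log-SD of 0.7, an equal fall to 0.64 in both analytes, and 20 men per arm. The documents do not support saying that the concentration comparisons are wrong, that a ratio test would always detect more, or that the ratio went unanalysed.

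**What to change.** Add a ratio analysis to the SAP, alongside the existing comparisons:

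- **Variable.** Within-sample log ratios of tenofovir to dATP and emtricitabine to dCTP (the sponsor should confirm the pairing), in PBMC and rectal samples at visit 4.
- **Contrast.** Truvada against Truvada + lubricant only; men on lubricant alone take no study Truvada.
- **Test.** Wilcoxon rank sum if all drug values are detected. Where drug is below the LOD, keep the sample, treat its ratio as left-censored at LOD/dNTP and use, for example, Gehan's test. Do not drop it or rank it lowest.
- **Estimate.** The ratio of ratios with a 95% CI from a censored log-normal model of drug and dNTP jointly, with a check of log-normality.
- **Undetectable dNTP, if any.** Use a bivariate model that censors both analytes, since a regression on log dNTP cannot take a censored covariate. Report counts by arm, including samples with both undetectable.
- **Specimen.** State which rectal material was assayed. If it was whole tissue, say that the ratio does not directly measure HIV target cells.
- **Status.** Label the analysis as added to the SAP but traceable to the protocol's aim. If a ratio was already analysed, state how.

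**Cost.** No new samples or assays; some modelling work and a later-added label. Two ratios in two compartments make four more comparisons. If independent and unadjusted, the chance of at least one false positive is 1 − 0.95^4 = 18.5%, so present them as estimates with CIs.

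### On its natural reading, the SAP's Wilcoxon test of dNTPs and immune cell proportions leaves the visit 2 baseline unused: a possible loss of precision, not a bias

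*SAP*

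**What the plan says.** The SAP is three sentences long. The one that describes the analysis reads "Detectable drug and dNTP concentrations as well as immune cell proportions were compared between" the three "study arms using a Wilcoxon Rank Sum Test". It names no visit, change score, baseline covariate, effect estimate or confidence interval. The protocol has no statistical section that supplies them.

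The protocol's sampling plan is richer:

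- **Design.** Visit 2 comes before any study product and consists of a blood draw plus "collection of rectal secretions, and rectal biopsy via rigid sigmoidoscopy for establishment of baseline values".
- **Project Description.** Blood, secretions and biopsies "will be collected from men in all three study arms at least 21 days prior to initiation of treatment", and again straight after seven days of product.
- **Project Description, flow cytometry.** The immune cell aim, which concerns HIV target cells and how activated they are, is worded as change: "rectal lymphocytes from 10 participants in each arm will be characterized using multicolor flow cytometry to observe potential changes in the proportion".

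**The concern.** Each man undergoes a sigmoidoscopy with 8-12 biopsies at visit 2 largely to provide a baseline, and the SAP does not say what that baseline is for. A between-arm test of visit 4 values alone leaves stable differences between men in the error term. Flow cytometry has only 10 men per arm, so intervals will be wide and only large differences can be detected. If a man's visit 2 and visit 4 values are well correlated, adjustment would narrow the intervals using data already in hand. If they are not, little or nothing is lost by the plan as written.

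**Working it through.** **1. The plan's own figure.** Neither document gives a power, effect size, SD or correlation. The only sample-size arithmetic is in Study Population: 70 men with 10-15% loss, giving 60 completers. 70 × 0.85 = 59.5 and 70 × 0.90 = 63, so it reproduces. This point does not rest on it.

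**2. Which visit is tested.** Design says that comparing assay results among the arms should show what lubricant does. That can only be seen after product use. Inclusion Criteria exclude men taking PrEP, so no drug is expected at visit 2. Visit 4 is therefore the natural reading, although the SAP does not state it.

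**3. Gap between the two measurements.** The Lay Summary puts visit 4 at least 4 weeks after visit 2. Visit 2 can fall at week 1 and visit 4 at week 26, so the gap can reach 26 − 1 = 25 weeks. A high r cannot be presumed.

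**4. Variance relative to visit 4 values alone** (equal variance at both visits):

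- Change from visit 2: 2(1 − r) = 2, 1.4, 1, 0.6 at r = 0, 0.3, 0.5, 0.7. This exceeds 1 whenever r is below 0.5.
- Baseline adjustment: 1 − r² = 1, 0.91, 0.75, 0.51, before the small cost of estimating a slope.

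**5. CI half-width, 10 per arm, three-arm model.** Unadjusted, with 27 residual degrees of freedom: 2.052 × √(2/10) × 0.991 = 0.909 SD, where 0.991 is the mean of the estimated SD relative to the true SD. With the covariate, the simulated half-width at r = 0 is 0.928 SD. In general it is 0.928 × √(1 − r²), giving 0.885, 0.80 and 0.66 SD at r = 0.3, 0.5 and 0.7. Break-even: √(1 − r²) = 0.909/0.928 = 0.980, so r is about 0.2.

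**6. Power, 10 per arm, assumed difference 1.2 SD.** Normal data, two-sided 0.05, 20,000 replicates:

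| r | 0 | 0.3 | 0.5 | 0.7 |
|---|---|---|---|---|
| Wilcoxon, visit 4 | 67% | 67% | 67% | 67% |
| Wilcoxon, change | 39% | 52% | 67% | 88% |
| Three-arm model, unadjusted | 74% | 73% | 73% | 74% |
| Three-arm ANCOVA | 72% | 75% | 83% | 94% |
| Rank ANCOVA, two arms | 67% | 71% | 77% | 89% |

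The like-for-like comparisons are ANCOVA with the unadjusted model, and two-arm rank ANCOVA with the Wilcoxon test. Setting ANCOVA against the Wilcoxon test would credit baseline with a gain that comes partly from the normal model and pooled variance. ANCOVA's type I error was 4.8-5.1%.

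**7. Other effect size and sample sizes.** At 10 per arm and 1 SD, Wilcoxon on visit 4 has 51-52% power; rank ANCOVA has 53, 55, 62 and 76%. dNTPs are measured in more men. At 20 per arm and 0.8 SD, the unadjusted model has 70% and ANCOVA 69, 73, 81 and 93%. At 26 per arm and 0.7 SD, it is 70% against 69, 74, 82 and 94%. The pattern does not depend on which enrolment figure is right.

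**8. Handling of incomplete baselines** (rates assumed; the documents give none). At 10 per arm, 1.2 SD and r = 0.5, with 2 of 10 baselines missing per arm, dropping those men gives 73%, so the gain is lost. Filling with the overall mean gives 81%. If the lowest 20% of baselines are undetectable, setting them to the assay limit gives 83%, against 77% for the overall mean.

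**The case against.** The strongest case against is that nothing in the plan is wrong. The visit can be inferred, a randomized comparison of visit 4 values is valid, and the benefit of adjustment rests on an r the documents do not give. At r = 0.3 it is worth 2-4 points of power; gains of 10 points or more need r of about 0.5, and a gap of up to 25 weeks makes that uncertain. The effect sizes above are assumed, and all the simulations use normal data, so gains with skewed assay data are untested. ANCOVA on transformed values also needs rules that a rank test does not: logit is undefined at 0 or 1, and log needs a value for an undetectable dNTP.

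Most of this stands. It limits the size of the claim and adds requirements to the fix. It does not remove the point, because the baseline is collected at real burden to participants, the cell aim is worded as change, and adjustment costs 1-2 points of power at worst.

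Two stronger readings are tempting. A reader might infer that omitting baseline biases the comparison; randomization rules that out. A reader might also infer that the unnamed visit leaves the analysis open; since Design points to visit 4, it is a missing label that one sentence repairs.

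**Conclusion.** The point holds as a matter of precision. The SAP's test is valid on its natural reading and leaves the visit 2 dNTP and cell values unused. Whether that costs anything depends on r: below about 0.2 nothing is lost, near 0.3 the loss is small, and from about 0.5 it is material (10 points of power or more, and a CI half-width of 0.80 SD or less instead of 0.91 SD at 10 per arm). These sizes assume normal data, equal variances, complete pairs and the stated differences. It is a worthwhile, inexpensive improvement.

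The documents do not support a claim that precision certainly is lost, since no r is given. Nor does the wording of the cell aim require a change-score analysis, which would be worse than visit 4 values alone when r is below about 0.5.

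Separate matters that add no weight here are the conflict between 90 men (Design) and 70 (Study Population), the protocol endpoints the SAP does not analyse (cytokines, in vitro infection, the drug-to-substrate ratio), and the restriction to detectable dNTP values.

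**What to change.** - Keep the Wilcoxon test and state that it uses visit 4 values.
- Add a supplementary ANCOVA of visit 4 log dNTP and logit cell proportion, with three-level arm and the man's visit 2 value on the same scale. Report adjusted differences with 95% CIs and the observed r.
- State an offset for proportions of 0 or 1 and a rule for undetectable visit 4 dNTPs. Baseline adjustment does not solve the latter.
- Use rank ANCOVA as the sensitivity analysis. It gives no difference on the measurement scale, so it should not be the main adjusted result.
- Keep every man with a visit 4 value. Fill visit 2 without regard to arm: the overall mean if missing, the assay limit if undetectable.
- Do not use change scores. Leave drug concentrations unadjusted, since entrants are not on PrEP and have no informative drug baseline.
- The SAP is written in the past tense. If results were known when the analysis is added, label it post hoc; otherwise label it supplementary.

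The cost is one SAP paragraph and modest programming, with no new visits or samples. The statistical downside is 1-2 points of power if r is near 0 (half-width 0.93 against 0.91 SD at 10 per arm).
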